## 2. LIST OF ABBREVIATIONS

AE	adverse event
ALT	alanine transaminase
ARR	annualized relapse rate
AST	aspartate transaminase
BPM	beats per minute
CBC	complete blood count
CD25	$\alpha$ subunit of interleukin-2
CD122	$\beta$ subunit of interleukin-2
CD132	$\gamma$ subunit of interleukin-2
CI	confidence interval
CIS	clinically isolated syndrome
CNS	central nervous system
CRF	case report form
CRO	contract research organization
DMF	Dimethyl Fumarate
DHA	Directions for Handling and Administration
DMT	disease-modifying therapy
DSMB	Data Safety Monitoring Board
EC	ethics committee
EDC	electronic data capture
EDSS	Expanded Disability Status Scale
EMA	European Medicines Agency
GA	glatiramer acetate
Gd	gadolinium
Gd+	gadolinium enhanced
HBcAb	hepatitis B core antibody
HBsAg	hepatitis B surface antigen
HCV Ab	hepatitis C virus antibody
HIV	human immunodeficiency virus
ICF	informed consent form
ICH	International Conference on Harmonisation
IFN- $\beta$	interferon $\beta$
IL-2	interleukin 2
IL-2R	interleukin 2 receptor
IM	intramuscular
IS	immunosuppressant
IRB	Institutional Review Board
ITT	intent-to-treat
IV	intravenous
JCV	John Cunningham Virus

CONFIDENTIAL

The information contained herein may not be used, disclosed, or published without the written consent of Biogen MA Inc.

LFT	liver function tests
MRI	magnetic resonance imaging
MS	Multiple Sclerosis
MSFC	Multiple Sclerosis Functional Composite
NEDA	no evidence of disease activity
NK	natural killer T cells
PD	pharmacodynamic
PHI	protected health information
PML	progressive multifocal leukoencephalopathy
RMS	Relapsing Multiple Sclerosis
RRMS	Relapsing-Remitting Multiple Sclerosis
SABR	safety and benefit-risk
SAE	serious adverse event
SAP	statistical analysis plan
SC	subcutaneous
SDMT	Symbol Digit Modalities Test
SGOT	serum glutamic oxaloacetic transaminase
SGPT	serum glutamic pyruvate transaminase
SUSAR	suspected unexpected serious adverse reactions
ULN	upper limit normal
US	United States

CONFIDENTIAL

The information contained herein may not be used, disclosed, or published without the written consent of Biogen MA Inc.

### 3. SYNOPSIS

Tracking number:	205MS305
Protocol Title:	A Phase 3b, 12-month, Open-label, Multicenter Study to Evaluate the Efficacy and Safety of BIIB019, Daclizumab, in Subjects with Relapsing-Remitting Multiple Sclerosis (RRMS) Switching from Natalizumab (SUSTAIN)
Version Number:	1.0
Name of Study Treatment:	Daclizumab (high yield formulation)
Study Indication:	Relapsing-Remitting Multiple Sclerosis (RRMS)
Phase of Development:	3b
Rationale for the Study:	The purpose of this study is to evaluate the efficacy and safety of daclizumab (high yield formulation) in subjects switching from natalizumab due to safety concerns. There is a need for clearer evidence-based guidelines on alternative therapy and management of subjects during and post-transition from natalizumab. With a well-established safety and efficacy profile, daclizumab can be considered a good therapeutic option for RRMS subjects treated with natalizumab, who decide to change therapy.
Study Objectives and Endpoints:	
Primary Objective
 
The primary objective of the study is to evaluate the effects of treatment with daclizumab on proportion of subjects relapse-free at 6 months, in RRMS subjects who switched from treatment with natalizumab to daclizumab due to safety concerns.
 
Primary Endpoint
 
The primary endpoint in relation to this objective is the proportion of subjects relapse-free at Month 6, in RRMS subjects treated with daclizumab who switched from treatment with natalizumab.

CONFIDENTIAL

The information contained herein may not be used, disclosed, or published without the written consent of  
Biogen MA Inc.

### Secondary Objectives

The secondary objectives of this study in this study population are to evaluate the effects of daclizumab on the following:

- Multiple Sclerosis (MS) relapse activity including annualized relapse rate (ARR) and the proportion of subjects experiencing relapses requiring hospitalization and/or steroid treatment.
- MS-related outcomes measured using magnetic resonance imaging (MRI).
- Safety and tolerability in subjects previously treated with natalizumab.

### Secondary Endpoints

The secondary endpoints of this study are the following:

- The proportion of subjects relapse-free at Month 12.
- The proportion of subjects experiencing relapse requiring hospitalization and/or steroid treatment at Month 12.
- The ARR at Month 12.
- The number of new gadolinium enhanced (Gd+) and T1 hypointense lesions at Month 6 and Month 12 on MRI.
- The number of new or newly enlarged T2 hyperintense lesions at Month 6 and Month 12 on MRI.
- The permanent discontinuation rate of daclizumab at Month 12.
- The incidence of adverse events (AEs) and serious adverse events (SAEs) including clinically relevant shifts in clinical laboratory assessments.

### Exploratory Objectives

The exploratory objectives of this study in this study population are to evaluate the effects of daclizumab on the following:

- 

CONFIDENTIAL

The information contained herein may not be used, disclosed, or published without the written consent of Biogen MA Inc.

- [REDACTED]
- [REDACTED]
- [REDACTED]

**Exploratory Endpoints**

The exploratory endpoints of the study include the following:

- [REDACTED]
- [REDACTED]
- [REDACTED]
- [REDACTED]
- [REDACTED]
- [REDACTED]
- [REDACTED]
- [REDACTED]
- [REDACTED]

CONFIDENTIAL

The information contained herein may not be used, disclosed, or published without the written consent of Biogen MA Inc.

•

Study Design:	This is a multicenter, open-label study of daclizumab monotherapy in subjects with RRMS who were previously treated with natalizumab for at least 12 months. Subjects will be enrolled over an approximately 12-month period. Subjects discontinuing from natalizumab treatment due to safety concerns will commence treatment with daclizumab following consent and evaluation of eligibility. Subjects will initiate treatment with daclizumab at 28 (+3) days following the last infusion of natalizumab. Assessments will be completed at enrollment, baseline, Month 1, Month 3, Month 4, Month 6, Month 9 and Month 12.
Study Location and Number of Sites:	Approximately 40 sites in the United States (US) and rest of world.
Number of Planned Subjects:	Approximately 100 subjects.
Study Population:	The study will enroll RRMS subjects aged 18 to 55 years who discontinued treatment with natalizumab due to safety concerns. Subjects must enroll into the study within 28 (+3) days after discontinuation, and have been treated with natalizumab for at least 12 months prior to screening. Subjects must not have missed 2 or more consecutive scheduled doses.
Treatment Groups	Daclizumab monotherapy administered using a pre-filled pen, also known as an autoinjector.
Duration of Treatment and Follow-up:	The duration of subject participation will be up to 16 months, including a 28 (+3) day screening period, treatment with daclizumab for up to 12 months, and an additional safety follow-up visit performed remotely 4 months after last study treatment dose. Subjects having tentative disability progression near the end of the core study (e.g., Month 12) will attend additional follow-up visits 12 and 24 weeks later to confirm progression.
Data Monitoring	An independent Data Safety Monitoring Board (DSMB) will monitor the benefit/risk throughout the trial.

CONFIDENTIAL

[figure not shown]
The information contained herein may not be used, disclosed, or published without the written consent of Biogen MA Inc.

## 4. STUDY SCHEMATIC AND SCHEDULE OF ACTIVITIES

### 4.1. Study Design

Figure 1: Study Design below provides a schematic for study 205MS305.

Figure 1: Study Design

**Abbreviations:** AE: adverse event; [REDACTED]; MRI: magnetic resonance imaging; MS: Multiple Sclerosis; SAE: serious adverse event.

CONFIDENTIAL

The information contained herein may not be used, disclosed, or published without the written consent of Biogen MA Inc.

## 4.2. Schedule of Assessments

The schedule of assessments is presented in [Table 1](#). Assessment time points include an enrollment visit, a baseline visit, and follow-up visits at Months 1, 3, 4, 6, 9 and 12. An additional safety assessment will be performed remotely 4 months after the last study treatment dose. Subjects who discontinue treatment early will still be evaluated during the safety follow-up visit (i.e., 4 months after treatment and study discontinuation). Subjects having tentative disability progression identified near the end of the core study (e.g., Month 12) will attend additional follow-up visits 12 and 24 weeks later to confirm progression.

Magnetic resonance imaging (MRI) scans will be performed at the enrollment visit (no later than 7 days prior to the first dose of daclizumab), and at Months 1, 4, 6 and 12. MRI scans will be performed under the supervision of a trained radiologist. Ad-hoc MRI scans may be performed as needed, such as in the event of a MS relapse, in order to rule out a progressive multifocal leukoencephalopathy (PML) diagnosis.

Blood chemistry and hematology assessments will be performed at baseline and at Months 1, 3, 6, 9 and 12. Hematology assessments will include a complete blood count (CBC). Liver function tests (LFT) [alanine transaminase (ALT)/ aspartate transaminase (AST)] will be done at enrollment and monthly visits. Bilirubin testing must be done together with the first AST/ALT test at the enrollment visit. Bilirubin testing must also be done if ALT/SGPT (serum glutamic pyruvate transaminase), or AST/SGOT (serum glutamic oxaloacetic transaminase)  $>3*$ upper limit of normal (ULN), since treatment must be permanently discontinued with the concomitant elevation of total bilirubin  $>2*ULN$ .

At the end of the study, liver monitoring will be done per routine clinical practice.

A safety follow-up visit at 4 months after the last dose of daclizumab provided by the study will be conducted remotely to evaluate potential delayed safety outcomes. The assessments during the additional safety follow-up period will include all safety endpoints described in [Table 1](#). Liver function tests (LFT) will be performed only if the subject is continuing daclizumab or if the subject is within 4 months since study treatment discontinuation, and monitoring is deemed appropriate by the Investigator.

CONFIDENTIAL

The information contained herein may not be used, disclosed, or published without the written consent of  

**Table 1: Study Schedule of Assessments**

Study Period	Screening		Study Follow-up							
Visit Number	1	2	3	4	5	6	7	8	9	10
Title	Enrollment (Day - [28+3] to -1)	Baseline (Day 0)	Month 1 (± 4 days)	Month 3 (± 4 days)	Month 4 (± 4 days)	Month 6 (± 4 days)	Month 9 (± 4 days)	Month 12 (± 4 days)	Month 15 Safety follow-up  (± 14 days)	Early discontinuation 
Informed consent 	X									
Inclusion/exclusion criteria	X									
Demographics	X									
Disease and medical history	X									
MS treatment history	X									
MRI 	X		X		X	X		X		
Pregnancy testing 	Monitor and record throughout the study									
Liver function testing (AST/ALT) 	X		X	X	X	X	X	X	X 	X
Concomitant medications and non-drug therapies	Monitor and record throughout the study									
██████████	X	X		X		X	X	X		X
Vital signs	X	X	X	X		X	X	X		X
Physical examination	X	X	X	X		X	X	X		X
██████████	X	X	X	X		X				
MS relapse assessment		X	X	X		X	X	X	X	X
Daclizumab dispensation/ administration 		X	X	X	X	X	X			

CONFIDENTIAL

The information contained herein may not be used, disclosed, or published without the written consent of Biogen MA Inc.

Study Period	Screening		Study Follow-up							
Visit Number	1	2	3	4	5	6	7	8	9	10
Title	Enrollment (Day - [28+3] to -1)	Baseline (Day 0)	Month 1 (± 4 days)	Month 3 (± 4 days)	Month 4 (± 4 days)	Month 6 (± 4 days)	Month 9 (± 4 days)	Month 12 (± 4 days)	Month 15 Safety follow-up  (± 14 days)	Early discontinuation 
Daclizumab dosing diary 						X	X			
Daclizumab accountability	Monitor and record throughout the study									
Hematology (CBC) 		X	X	X		X	X	X		X
Blood chemistry 		X	X	X		X	X	X		X
		X	X	X		X	X	X		
		X				X		X		
		X	X	X		X	X	X		
AEs/SAEs	Monitor and record throughout the study									

**Abbreviations:** MS: Multiple Sclerosis; MRI: magnetic resonance imaging; [REDACTED]; CBC: complete blood count; ALT: alanine transaminase; AST: aspartate transaminase; NK: natural killer T-cells; [REDACTED]; AE: adverse event; SAE: serious adverse event.

CONFIDENTIAL

The information contained herein may not be used, disclosed, or published without the written consent of Biogen MA Inc.

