## Efficacy and Safety of Daclizumab in Subjects with RRMS Switching from Natalizumab

1. Written informed consent must be obtained prior to start of the study.
2. Screening MRI should occur no later than 7 days prior to the first dose of daclizumab. For subsequent visits, MRI scan can be performed up to 4 days prior to the visit. Ad-hoc MRIs may be conducted as needed, such as in the event of a relapse to rule out PML diagnosis.
3. This is required only for females of child-bearing potential. A urine pregnancy test will be performed monthly.
4. Liver function tests (LFTs) are required to be performed monthly (either on-site or via home visits at Month 7, 8, 10 and 11, if applicable), and samples will be analyzed centrally for the purposes of this study. Results from either local or central LFT tests can be used for medical management of the patient and to determine whether dosing should continue or be suspended at the monthly dosing timepoint. In cases where local LFTs were performed, samples must also be collected for central analysis.
5. Liver function tests (LFTs) during the safety follow-up will be performed only if the subject is continuing daclizumab or if the subject is within 4 months since study treatment discontinuation, and monitoring is deemed appropriate by the Investigator; Abnormal AST/ALT values as described in the product label will lead to treatment suspension or discontinuation.
6. [REDACTED]
7. Samples will be analyzed centrally.
8. Daclizumab dosing will start at baseline and occur monthly until Month 11. Doses at baseline and Months 1, 2, 3, 4, 5, 6 and 9 will be administered in the clinic, and doses at Months 7, 8, 10 and 11 can be administered at home or in the clinic. Daclizumab dosing will not begin until a minimum of 28 days have passed since last natalizumab dose. Before a monthly dose of daclizumab is given, LFT results from a prior test performed within the previous 28 (+3) days must be reviewed by the Study Neurologist or their backup.
9. Subjects will be provided a dosing diary at the Month 6 and Month 9 visits to record observations for home dosing only; home dosing is possible for Month 7, 8, 10, and 11. A window of  $\pm 4$  days applies to daclizumab dose even if it is done at home; subjects should be appropriately instructed on daclizumab self-administration using the autoinjector.

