### 5.2.1. Rationale for Duration between Therapies

As part of the study design, subjects must receive their first dose of daclizumab at 28 (+ 3) days following discontinuation of natalizumab. The rationale for this requirement is to minimize the washout period between daclizumab and natalizumab. Clinical research studies in patients switching from natalizumab to an alternative treatment option have shown that disease activity can occur within the first 6 months of discontinuing natalizumab. However, in several of these studies, the risk of disease recurrence was shown to be mitigated with a shorter washout period between treatments [Cohan 2015; Kappos 2015c]. In a randomized trial evaluating the effects of natalizumab treatment interruption (RESTORE), it was shown that natalizumab concentrations reach undetectable levels 8 weeks after discontinuation [Cree 2013]. Pharmacodynamic (PD) studies with daclizumab demonstrated increases in CD56bright NK cells and serum IL-2 levels within the first 4 weeks of treatment [Amaravadi 2015] and effects on disease activity, as evidenced by reductions in Gd+ lesion activity, were apparent within 8 to 12 weeks (SELECT; Biogen, data on file). These data indicate that a 28-day gap between the discontinuation of natalizumab and the initiation of daclizumab would maximize the PD overlap of these 2 therapies and thus minimize the amount of time patients are not protected by a highly efficacious therapy.

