## **10. STUDY TREATMENT**

Biogen MA Inc. will provide daclizumab to sites in the US. Biogen Idec Research Limited will provide daclizumab to sites in all other countries. Daclizumab must be administered on-site during the first 6 months, and at the Month 9 visit. Sites have the option to allow subjects to administer the drug at home for doses at Month 7, 8, 10, and 11.

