5 STATISTICAL ANALYSES

5.1 Primary Analysis

Definition of relapses. Relapses are defined as new or recurrent neurological symptoms not associated with fever or infection, lasting at least 24 hours, and accompanied by new objective neurological findings upon examination by the Examining Neurologist. Protocol-defined relapses up to the end of treatment period visit will be included in the primary analyses. New or recurrent neurological symptoms that occurred less than 30 days following the onset of a protocol-defined relapse will be considered part of the same relapse (i.e., relapses with onset days ≤ 29 days of one another, will be counted as 1 relapse).

Censoring. If a subject prematurely discontinues the treatment and the subject does not experience a protocol-defined relapse prior to discontinuation, the subject will be censored on the last dosing date.

Analysis method. The number of relapses per subject will be summarized. The proportion of subjects who are relapse-free at 6 months will be estimated as 1 minus the cumulative

probability of relapses from the Kaplan-Meier product limit method. The time to relapse is the number of days from the first dosing date to the date of first relapse, or end of treatment period, whichever comes first. Time to first relapse will be summarized by 10th, 25th and 50th percentile.

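### Table 1 schedules no MS relapse assessment between Month 3 and the Month 6 primary time point, so capture there depends mainly on the subject making contact

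*Protocol*

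**What the plan says.** Protocol Section 4.2 lists "follow-up visits at Months 1, 3, 4, 6, 9 and 12". In Table 1 the row "MS relapse assessment" is marked at Baseline, Months 1, 3, 6, 9 and 12, the Month 15 safety follow-up and early discontinuation. The Month 4 cell is blank.

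The subject is nevertheless on site at Month 4:
- **MRI:** Section 4.2 schedules scans at enrollment "and at Months 1, 4, 6 and 12".
- **Liver tests:** Table 1 marks one at Month 4, and footnote 4 says "Liver function tests (LFTs) are required to be performed monthly".
- **Dosing:** footnote 8 says "Doses at baseline and Months 1, 2, 3, 4, 5, 6 and 9 will be administered in the clinic", and Section 10 says "Daclizumab must be administered on-site during the first 6 months, and at the Month 9 visit". Months 2 and 5 are thus also clinic attendances, although Table 1 has no column for them.

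Between scheduled assessments, Section 10.5 tells a subject with a suspected relapse to contact the Study Neurologist within 48 hours of onset, with evaluation to follow within 72 hours. Table 1 has adverse events and concomitant medications recorded continuously.

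The primary endpoint is the proportion relapse-free at Month 6, estimated by Kaplan-Meier from first dose to the date of first relapse. SAP 5.1 counts a relapse only if it is "accompanied by new objective neurological findings upon examination by the Examining Neurologist".

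**The concern.** The second half of the primary-endpoint window has no planned occasion for asking about relapse, although the subject is in the clinic at Months 4 and 5. Capture in that half depends mainly on the subject recognising symptoms and calling.

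The SAP definition makes timing matter. If a relapse is not reported promptly and its signs have gone by Month 6, there may be nothing left to find on examination, and the event does not count. A first relapse lost in this way either raises the relapse-free proportion or, if a later relapse before Month 6 is confirmed, leaves it unchanged. It cannot lower it. In a single-arm, open-label study no control group shares the same loss.

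The period is relevant to the question asked: Section 5.2.1 notes that "disease activity can occur within the first 6 months of discontinuing natalizumab".

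**Working it through.** **1. The plan's precision figure.** Section 13.1 gives 100 subjects, 10% drop-out, 90 evaluable, and 95% half-widths of 8.3 and 6.7 points at 80% and 88% relapse-free. The normal-approximation half-width is 1.96 × √(p(1−p)/n), with n = 100 × 0.90 = 90:
- p = 0.80: 1.96 × √(0.80 × 0.20/90) = 8.26 points.
- p = 0.88: 1.96 × √(0.88 × 0.12/90) = 6.71 points.

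Both agree with the protocol. They serve here only as a yardstick, since the relapse schedule does not affect them.

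**2. Scheduled intervals.** One month is 365.25/12 = 30.4 days. The upper figure adds 8 days for a ±4-day window at each end.

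| Relapse assessments up to Month 6 | Longest interval | Days (with windows) |
|---|---|---|
| As in Table 1: 0, 1, 3, 6 | Month 3 to 6 | 91 (99) |
| Month 4 added: 0, 1, 3, 4, 6 | 2 months | 61 (69) |
| Every in-clinic dose: 0, 1, 2, 3, 4, 5, 6 | 1 month | 30 (38) |

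**3. Possible size.** The protocol's expected 80% to 88% relapse-free means that 12% to 20% relapse by Month 6. Two further inputs are assumptions with no source in the documents: half of those relapses start in Months 3 to 6, and 10% to 30% of these are not reported in time for an examination.
- Low end: 100 × 0.12 × 0.5 × 0.10 = 0.6 subjects per 100.
- High end: 100 × 0.20 × 0.5 × 0.30 = 3.0 subjects per 100.

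**4. Check on the assumed half.** Under a constant hazard, the proportion with a first relapse in Months 3 to 6 is √p − p.
- p = 0.80: 0.894 − 0.800 = 0.094, or 8.5 of 90 subjects and 47% of the relapses by Month 6.
- p = 0.88: 0.938 − 0.880 = 0.058, or 5.2 of 90 subjects and 48%.

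One half is therefore a fair approximation. With 10% to 30% missed, the upward bias is 0.9 to 2.8 points at 80% and 0.6 to 1.7 points at 88%. With 5% missed it is 0.5 and 0.3 points.

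**5. What a Month 4 check alone could reach.** It can pick up only onsets in Months 3 to 4, which is one of the three months. Under a constant hazard that is 2.9 of the 8.5 relapses at 80% and 1.8 of the 5.2 at 88%, about a third in each case. A third of 0.6 to 3.0 is 0.2 to 1.0 per 100. This is an upper limit, because signs must still be present when the subject is examined.

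**The case against.** The strongest defence is that the plan does have a route for relapses between visits. Section 10.5 names suspected relapse, sets the 48-hour and 72-hour limits, and says such subjects should not take further daclizumab until evaluated. Continuous recording of adverse events and concomitant medications could bring a relapse, or steroids given for it, to light. Section 11.2.2.4 collects the onset date separately from the visit date, so a late report can be dated correctly. All of this stands. A reader might infer that relapses in Months 3 to 6 are not ascertained at all. The documents do not support that: the gap is in scheduled assessment only.

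A reader might also infer that the protocol treats this as its most critical window. Section 5.2.1 says only that activity can occur in the first 6 months after natalizumab and ranks no period. Daclizumab starts about one month after the last infusion, so study Months 3 to 6 are roughly months 4 to 7 off natalizumab, and about a third of the gap lies beyond the period cited.

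Further, the relapse definition in Section 11.2.2.4 of the protocol requires no objective finding. A resolved relapse recalled at Month 6 would meet it and is lost only through the SAP's added requirement. That mismatch is a separate issue, but the SAP governs the primary analysis, so the loss remains.

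Finally, Month 4 is evidently a light visit, with vital signs, physical examination, hematology and chemistry also blank, and 3-month intervals recur after Month 6. That may explain the omission, but the documents give no reason for it. The Month 3 to 6 interval differs from the later ones in that it ends at the primary time point.

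**Conclusion.** The point holds as a gap in scheduled assessment, of minor to moderate severity. No relapse assessment is scheduled for about 91 days before the primary time point, half of the 6-month window. Combined with the SAP definition, any resulting loss can only favour the relapse-free proportion.

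The plausible size is 0.6 to 3 points over Months 3 to 6, which stays below the planned half-widths of 6.7 to 8.3 points. It rests on the assumed 10% to 30% non-reporting and the assumed half of relapses falling in those months. It would be wrong to attribute the full range to the blank Month 4 cell, which accounts for at most about 0.2 to 1 point; the rest concerns onsets after Month 4. Sample size, type I error and interval width are unaffected.

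The SAP records that the study was terminated after approximately 30 subjects were enrolled. One misclassified subject in 30 would move a simple proportion by 1/30 = 3.3 points, but on the same assumptions the expected number is only 30 × 0.006 = 0.2 to 30 × 0.03 = 0.9.

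**What to change.** Mark the relapse assessment at Month 4 in Table 1, and add a brief relapse query at each in-clinic dosing attendance through Month 6, which brings in Months 2 and 5. A positive answer goes to the Study Neurologist evaluation that Section 10.5 already describes. The Month 4 mark alone shortens the longest interval before the endpoint from about 91 to 61 days; with the dosing queries it falls to about 30.

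The cost is a short CRF entry and a few minutes at attendances that already take place, plus a few extra unscheduled neurological examinations. Months 2 and 5 have no column in Table 1, so the query there needs a footnote or new columns as well as the single cell.

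For this study the schedule can no longer be changed. The abbreviated report should state that no relapse assessment was scheduled between Months 3 and 6, and that the Month 6 estimate may be biased upward for that reason. The schedule change is for any later study of the same design.
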